2. STUDY OBJECTIVES AND ENDPOINTS

Objectives	Endpoints

Primary
 
 To evaluate whether educational workshops paired with self-collected hrHPV screening will increase participation in cervical cancer screening among Southeast Asian (Hmong, Burmese, Karen, and Karen) refugee and immigrant populations in Wisconsin compared with offering clinician-collected screening. 	
 Uptake of cervical cancer screening using a self-collect device vs. clinician-based screening.

Secondary
 
 To evaluate participant satisfaction with the educational workshops using satisfaction surveys. To evaluate participant willingness to use self-collection as method for screening. 	
 Participant satisfaction as determined using qualitative methods. General willingness to use a HPV self-collect device at home and/or as the preferred collection method for cervical cancer screening, assessed via mixed methods survey.

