9. PROCESS TO DOCUMENT CONSENT IN WRITING

This study requests of waiver of written documentation of consent

- A written script of the information will be provided orally.
- Pre-recorded video of oral script will be available to all participants for future reference.
- Research presents no more than minimal risk of harm to subjects.
- The research involves no procedures for which written consent is normally required outside of the research context.

This consent requests an alteration of the consent process (HRP-410) due to the following criteria:

- The study involves no more than Minimal Risk to the participants based on clinical standard of care.
- The study could not be practically carried out without the alteration. Participants will be blinded to which group they are randomized in order measure participation rates based on which type of screening method they are offered (clinician-collection vs self-collection)
- The alteration will not adversely affect the rights and welfare of the subjects. Participants will be provided the risks of each collection method in detail during the workshops. If a participant declines the type of screening they are offered will then be offered the other screening method.
- Subjects will be provided the additional pertinent information after participation.
- High proportion of participants in this study population have no or low reading or writing literacy in English or the native language.

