APPENDIX C: UW Health Researchers Post-Workshop Satisfaction Survey (UW-PSS)

Due to the number of skip logics, the survey is best viewed through Qualtrics

Link: https://uwmadison.co1.qualtrics.com/jfe/form/SV_bQT22KcJ9g7Qklw

Community Health Outreach to Increase Cervical Cancer Education and Self-Collection Screening (CHOICES) Program among Burmese and Hmong Women in Wisconsin.

This post-workshop participant survey is designed to be filled out with the guidance of Community Health Workers.

Please do not have the participant fill this information on their own.

Please copy the below information from the paper MCHH intake form:

Section A

After today's workshop, how likely are you to....?

	Not Likely	Somewhat unlikely	Neutral	Somewhat likely	Very Likely
1) Receive a Pap/Pelvic exam this year or as recommended?					
2) Spread the word about the screenings available to your family members?					
3) To encourage your family members to get screened?					
4) Practice healthy behaviors that can reduce your risks of cervical cancer?					

What workshop did the participant attend?

Clinician-collection education → Continues to Section B

Self-collection education → Skip to Section D

Section B

Did the participant get screening for cervical cancer today? (Clinician Collected)

Yes

No → Skip to Section C

Section B (continued)

How comfortable did you feel with this method?

- Extremely comfortable
- Somewhat comfortable
- Neither comfortable nor uncomfortable
- Somewhat uncomfortable
- Extremely uncomfortable

How likely would you get screening for cervical cancer again?

- Extremely likely
- Somewhat likely
- Neither likely nor unlikely
- Somewhat unlikely
- Extremely unlikely

In the workshop you attended today, we did not discuss self-collection as an option.

If self-collection was an option, would you have preferred this method?

- Yes
- Maybe
- No

Any remaining questions you have about the workshops or about cervical cancer?

Survey End

Section C

Will you get screening for cervical cancer in the near future (within the next year)?

- Yes
- Maybe
- No

Do you have any concerns with getting screening for cervical cancer?

[figure not shown]
Where would you go to get cervical cancer screening?

- My usual doctor or other clinician
- The health department
- Will return to the community center
- Another health care provider (not yet found)
- Not sure yet

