Section C (continued)

In the workshop you attended today, we did not discuss self-collection as an option.

If self-collection was an option, would you have preferred this method?

Yes

Maybe

No

→ Any remaining questions you have about the workshops or about cervical cancer? **Survey End**

At this time - please provide a quick 1 on 1 instruction on self-collection for cervical cancer screening.

After the participant is done, please return to complete the remainder of this survey.

Patient agreed and collected a self sample → Skips to to Section E

Patient declined a self sample today

→ Any remaining questions you have about the workshops or about cervical cancer? **Survey End**

Section D

Did the participant get screening for cervical cancer today? (Self Collected)

Yes, clinician collection → Skips to to Section F

Yes, self-collection → Skips to to Section E

No → Skips to to Section G

Section F

How comfortable did you feel with this method?

Extremely comfortable

Somewhat comfortable

Neither comfortable nor uncomfortable

Somewhat uncomfortable

Extremely uncomfortable

How likely would you get screening for cervical cancer again?

Extremely likely

Somewhat likely

Neither likely nor unlikely

Somewhat unlikely

Extremely unlikely

Any remaining questions you have about the workshops or about cervical cancer?

Survey End

Section E

How comfortable did you feel with this method?

- Extremely uncomfortable
- Somewhat uncomfortable
- Neither comfortable nor uncomfortable
- Somewhat comfortable
- Extremely comfortable

How likely would you do self-collection for cervical cancer screening again?

- Extremely unlikely
- Somewhat unlikely
- Neither likely nor unlikely
- Somewhat likely
- Extremely likely

Would you have preferred a clinician to help with the collection?

- Do not prefer
- Prefer slightly
- Prefer a moderate amount
- Prefer a lot
- Prefer a great deal

Did you have any confusion with the instructions?

- No
- Yes

How likely are you to recommend this method to others?

- Extremely unlikely
- Somewhat unlikely
- Neither likely nor unlikely
- Somewhat likely
- Extremely likely

Any remaining questions you have about the workshops or about cervical cancer?

Survey End

Section G

Will you get screening for cervical cancer in the near future (within the next year)?

- Yes
- Maybe
- No

Do you have any concerns with getting screening for cervical cancer?

Where would you go to get cervical cancer screening?

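### As printed, the survey asks no self-collection willingness question of intervention women who did not self-collect, and no direct question about satisfaction with the workshop

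*Combined protocol and SAP*

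**What the plan says.** Section 2 lists two secondary objectives that rest on surveys: satisfaction with the educational workshops, and willingness to use self-collection. The endpoint for the second is "General willingness to use a HPV self-collect device at home and/or as the preferred collection method for cervical cancer screening". The endpoint for the first is satisfaction determined by qualitative methods. Section 13.1.3 has every participant answer both surveys whether or not she was screened, and gives the UW-PSS the role of covering what remains to be asked about satisfaction. Section 13.1.3.2 lists method preference among the survey themes, without tying it to particular women, and refers to Appendix C for the full survey.

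In Appendix C everyone answers Section A, and control women then go to B or C. Both of those sections ask "If self-collection was an option, would you have preferred this method", after the lead-in "In the workshop you attended today, we did not discuss self-collection as an option". Intervention women go to Section D, which records the method used that day and routes them on: self-collectors to E, the others by "Yes, clinician collection → Skips to to Section F" or "No → Skips to to Section G". Section E asks, among other things, "How likely would you do self-collection for cervical cancer screening again" and "Would you have preferred a clinician to help with the collection".

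Sections 13.1.3.2 and 16.2 say that survey answers are anonymous and not tied to the study identifier.

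**The concern.** The intervention arm is where women are taught about self-collection and offered it. The women there who did not take it up are the ones whose willingness is least obvious, and the printed form does not ask them. A willingness figure for that arm would describe only women who had just self-collected. In the control arm, by contrast, the question goes to screened and unscreened women alike. Because the survey is anonymous, nobody can go back later and fill the gap.

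Workshop satisfaction is a stated objective, but the form has no question that asks for it. The report would have to rely on items about other things.

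**Working it through.** The plan gives no figure to reproduce on this point. The check sets the printed survey sections side by side and counts the items on willingness to self-collect or preferred method (do it again, preference, recommend to others).

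| Route | Who | Other items | Self-collection willingness or preference items |
|---|---|---|---|
| A | Everyone | Four post-workshop intentions | 0 |
| B | Control, screened by clinician | Comfort, screen again | 1 |
| C | Control, not screened by clinician | Future screening, concerns, where | 1 (same as B) |
| E | Self-collectors (intervention, and control women who accept the later offer) | Comfort, confusion with instructions | 3 (do again, preferred a clinician, recommend) |
| F | Intervention, chose clinician | Comfort, screen again | 0 |
| G | Intervention, not screened | Future screening, concerns, where | 0 |

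All routes end with an open invitation to raise remaining questions. So 0 of 2 control routes and 2 of 3 intervention routes lack a self-collection willingness item, and no such item is common to B, C, E, F and G. The E items differ from the B and C item in wording and scale.

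Workshop satisfaction: 0 direct items. The comfort items rate the collection method, Section A asks about intentions, and the closing item asks for remaining questions. Home use: 0 items on any route.

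Wording of the control question: Section 11 describes a survey question on whether the woman would want to take her own sample if given the choice, and ties an offer of self-collection to a yes. Sections B and C instead ask whether she would have preferred that method. The Section 11 wording is not in the printed form.

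Number of women, as illustration only. Inputs: n = 125 per arm and uptake u from 0.77 to 0.94, the lowest and highest detectable rates in the Section 20.2 table (not expected values). The share c of screened intervention women who choose the clinician is assumed, because the documents give none.

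Not asked = n × (1 − u × (1 − c))

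- c = 0: 125 × 0.23 = 28.75, and 125 × 0.06 = 7.5
- c = 0.10: 125 × (1 − 0.693) = 38.4, and 125 × (1 − 0.846) = 19.3
- c = 0.20: 125 × (1 − 0.616) = 48.0, and 125 × (1 − 0.752) = 31.0

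**The case against.** The strongest reply is that behaviour already answers the question. Section D records the method chosen. Section 11 makes clinician collection available in the intervention arm, and Section 9 adds: "If a participant declines the type of screening they are offered will then be offered the other screening method". A woman in F has therefore shown her preferred method for that day, and a woman in G should have been offered both methods and declined both. This stands as partial evidence, and it is strongest for F. But a same-day choice is not general willingness or willingness at a future screening. The form itself draws that line when it asks unscreened women about the next year, and when it asks control women just screened by a clinician whether they would have preferred self-collection. The open question on concerns in G is about screening, not self-collection.

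Second, the form in use may differ. Appendix C says that the survey is best viewed online, its heading names a narrower population than the current title, and its control question differs from Section 11. This is a fair limit, and the reason to check the live form before anything else. Still, Section 13.1.3.2 presents Appendix C as the full survey, so a mismatch would itself need correcting.

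Third, satisfaction is to be judged by qualitative methods, and the intake form has an evaluation block with a comments line. That is true, but the comments line concerns cervical health, and qualitative data still need a question that prompts for satisfaction. The right statement is that no direct question exists, not that nothing relevant is collected.

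Fourth, coverage of control women is not complete either. Section 15 allows for women who do not complete surveys, and Section 13.1.4 removes those with a positive pregnancy test from the rest of the study. Hence the comparison here is of routes on the form, not of women answering.

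**Conclusion.** The point holds for Appendix C as printed. Stated willingness to self-collect would be reported in the intervention arm from self-collectors only, and workshop satisfaction has no direct question. The firm size is the item count: none in F and G, one in B and C, three different ones in E. The counts of women rest on borrowed detectable rates and assumed clinician shares, and they only illustrate.

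Three stronger readings are tempting, and the documents do not support them.

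- A reader might infer a biased between-arm test. Section 20.3.2 lists tests by type of data but names no willingness variable or contrast, and nothing in the documents gives a size or direction of bias.
- A reader might infer that these women are asked nothing about willingness. Intention to be screened is asked of everyone in Section A and again in F and G; what is missing is willingness to self-collect.
- A reader might infer that home use is a required component left unmeasured. The endpoint joins it with an and/or, so this is a loose end.

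The result is incomplete coverage of secondary, descriptive endpoints in a self-described pilot. The primary outcome is not touched by this point. It is worth fixing because the remedy is cheap and the answers cannot be recovered afterwards.

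**What to change.** 1. Compare the live Qualtrics form with Appendix C. Reconcile the Section 11 and Appendix C wording so that the documents show one control question and state which answer leads to the self-collection offer. The investigators must settle which; none is proposed here.
2. Use that single reconciled question for control women, with no near-duplicate beside it. Add an identically worded item about future screening, with the same response options, to F and G, and to E for intervention self-collectors. Leave out the lead-in saying that self-collection was not discussed, which would be untrue for these women. Control women who reach E have already answered in C.
3. State in Section 20.3.2 that stated willingness will be shown as the proportions answering Yes, Maybe and No, by arm, among women who complete the survey, beside the method chosen. Call it descriptive only, because control women answer before any self-collection instruction and intervention women after it.
4. Add to Section A one question on satisfaction with the workshop, with free text.
5. Add a home-use item, or remove home use from the endpoint.

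The cost is a few short translated questions, an edit to the form and appendix, and an IRB amendment. Answers already collected from women in F and G stay incomplete, and the report should say so.

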3. STUDY PARTICIPANTS

Study participants in this project include participants recruited for cervical cancer CHW-led educational workshops led by MCHH. Participants can be either Hmong, Karen, Burmese or Karen speaking and are recruited by MCHH with a particular focus on those who are behind or have never had cervical cancer screening. The main objective is to provide education to these participants on cervical cancer prevention and screening with subsequent invitation for immediate post-workshop sample collection for cervical cancer screening.

4. NUMBER OF PARTICIPANTS

Total number of study subjects: 250.

5. INCLUSION AND EXCLUSION CRITERIA

5.1 Inclusion Criteria

- Female (assigned female at birth, regardless of gender identity)
- Ages 25-65
- Fluent understanding in English, Karen, Burmese, Hmong or Karen.

5.2 Exclusion Criteria

- Prior hysterectomy
- Impaired decision-making capacity
- Pregnancy

6. SPECIAL POPULATIONS

Those who lack consent capacity, the mentally ill, prisoners, cognitively impaired persons, children, and employees will not be included in this research study.

7. RECRUITMENT METHODS

Participants will be identified and recruited by MCHH using several recruitment strategies.

7.1 Verbal Communication

Word of mouth among participants, family members, and the Southeast Asian community will be used. Participants will be encouraged to contact MCHH for further details and specifics about the research study.

Announcements at church service will be done by CHWs at local churches frequented by Southeast Asian immigrant and refugee communities. Announcements will be scripted and will include key eligibility, criteria, length of workshop, location of study site, type of remuneration, and contact details for further information.

7.2 Telephone Recruitment

The study team will call potential participants using a list of community members who have previously sought services through MCHH. Attempts to reach participants will be two times over a two-week period. All initial discussion with participants from recruitment lists, or when potential subjects contact the study team via other recruitment methods, will include a brief description of the study's purpose, eligibility criteria, and participant involvement will be reviewed. This must also include a statement that participation is voluntary. The screener will ask the caller if she has any questions and whether they are interested in participating. After all questions have been answered, the study team member will ask if the potential subject is interested in proceeding to the next step in recruitment for the study. Potential subjects will answer pre-screening questions using an IRB-approved script. Information collected from potential subjects who fail pre-screening will be destroyed at the end of the study period. Potential subjects who meet all pre-screening criteria will be invited to a particular workshop day in order to go through the consent process.

7.3 Participant Remuneration

All participants regardless of their participation in the post-workshop screening for cervical cancer or the post-workshop satisfaction survey will receive a \$25 gift card.

8. CONSENT PROCESS

The informed consent process will make clear that participation in any and all aspects of the study are voluntary, and that participants may end their participation at any time.

The informed consent process will be conducted following all federal and institutional regulations relating to informed consent. Informed consent will be obtained at the beginning of participation through the following process:

- A link to a pre-record video will be provided to each participant at the time of recruitment. This video will be created prior to the start of the study which CHWs employed through MCHH will provide consent information using the pre-approved oral script.
 - o If the CHW does not speak the spoken language, then the CHW would follow the script in English and a translator would then translate the information to the participant language.
- Upon arrival to the study, participants will be asked if they have seen the pre-recorded video:
 - o If any participant reports the video was not viewed – it will be shown to all participants.
 - o CHW provides a summary about the study, study activity, and consent items, then answering any questions which may arise.

- If the CHW does not speak the spoken language, then an the CHW would provide the information in English and a translator would then translate the information to the participant language. Questions or comments will also be translated back to the CHW to be answered. The translator will serve as witness to ensure that study materials and consent were understood by the participant.
- It will be noted in a participant's study record noting they provided verbal consent.

Participants will be informed of random assignment into two groups: standard-of-care control group and intervention group. Due to the nature of this study, we will not disclose which group the participant belongs to although will provide a debrief session at the end of the study about what information could not be given at the time of consenting, and why they could not be told at that time.

Participants will not be told the full procedures prior to enrollment due to the need to test the hypothesis in this study. Participants in the control group are initially only provided educational materials about the standard of care for cervical cancer screening. While self-collection may or may not be known by the workshop participants in the control group, this is not standard of practice nor usually recommended by clinicians. Whereas the intervention group is provided additional materials about self-collection in the core educational material and is offered as a screening option immediately at the end of the workshop. The uptake of cervical cancer screening by workshop participants at the end of the workshop will then be compared between these two groups to determine.

The informed consent process will include contact information for the PI, who can be contacted if participants or potential participants have questions or concerns.. Informed consent forms will be available in written English, Hmong, or Karen for reference only. All participants will have access to the pre-recorded video in their native language for reference.

9. PROCESS TO DOCUMENT CONSENT IN WRITING

This study requests of waiver of written documentation of consent

- A written script of the information will be provided orally.
- Pre-recorded video of oral script will be available to all participants for future reference.
- Research presents no more than minimal risk of harm to subjects.
- The research involves no procedures for which written consent is normally required outside of the research context.

This consent requests an alteration of the consent process (HRP-410) due to the following criteria:

- The study involves no more than Minimal Risk to the participants based on clinical standard of care.
- The study could not be practically carried out without the alteration. Participants will be blinded to which group they are randomized in order measure participation rates based on which type of screening method they are offered (clinician-collection vs self-collection)
- The alteration will not adversely affect the rights and welfare of the subjects. Participants will be provided the risks of each collection method in detail during the workshops. If a participant declines the type of screening they are offered will then be offered the other screening method.
- Subjects will be provided the additional pertinent information after participation.
- High proportion of participants in this study population have no or low reading or writing literacy in English or the native language.

